#### **4.1 “Typical” Respiratory Pathogens**

Sputum samples will undergo a microscopic examination. Microscopic examination of Gram-stained sputum specimens will be performed by the local/regional laboratory. Gram's stain slides will be sent to the central laboratory for a confirmatory reading. The stained slide read by the local/regional laboratory as well as an unstained slide will be sent to the central laboratory. The best Gram stain reading from the central read of a central laboratory Gram stained respiratory specimen and the central read of the local/regional laboratory Gram stained respiratory specimen will be used to determine the adequacy of the specimen for pathogen determination. If the Gram stain reading from the central read of a central laboratory Gram stained respiratory specimen and the central read of the local/regional laboratory Gram stained respiratory specimen have the same

ranking, the central read of a central laboratory Gram stained respiratory specimen will be considered the best Gram stain. The central reads of polymorphonuclear neutrophils (PMNs)/low power field (LPF) and squamous epithelial cells (SECs)/LPF ranked best to worst are as follows:

1. >25 PMNs/LPF and <10 SECs/LPF
2. 10-25 PMNs/LPF and <10 SECs/LPF
3. <10 PMNs/LPF and <10 SECs/LPF
4. >25 PMNs/LPF and 10-25 SECs/LPF
5. 10-25 PMNs/LPF and 10-25 SECs/LPF
6. <10 PMNs/LPF and 10-25 SECs/LPF
7. >25 PMNs/LPF and >25 SECs/LPF
8. 10-25 PMNs/LPF and >25 SECs/LPF
9. <10 PMNs/LPF and >25 SECs/LPF

If neither of the central reads is available, the local/regional read of the local/regional laboratory Gram stained respiratory specimen will be used.

In general, the central lab identification of genus and species will be used. If the local laboratory grows an isolate but the central laboratory is not able to grow the isolate, if isolates were lost during transportation or storage, or there are major discrepancies between the local and central laboratory in the identification of species, the central laboratory will request the local laboratory to resend the isolate. If the central laboratory identification remains unavailable for an isolate after the lab has requested the isolate be resent, the local laboratory identification will be used. For any discrepancies in genus and/or species identification between the central and local laboratory, the central laboratory identification will be used as the default identification. Thus, it is possible for subjects to have different isolates from both central and local laboratories as a result.

*Streptococcus pneumoniae*, *Haemophilus influenzae*, *Staphylococcus aureus* and *Moraxella catarrhalis* will always be considered a CABP pathogen in the presence of the following criteria:

**Streptococcus pneumoniae**

- Positive BAL, pleural fluid or blood culture; or
- Positive sputum culture in the presence of a Gram stain with >25 PMNs/LPF and <10 SECs/LPF (**NOTE:**  $\geq 10$  PMNs/LPF and <10 SECs/LPF in the expanded Microbiological ITT (emicroITT) Analysis Set); or
- Positive urinary antigen test; or
- Positive real-time quantitative Polymerase chain reaction (RQ-PCR) of nasopharyngeal swab or sputum (see [Table 1](#) for cutoff values); or
- Positive nasopharyngeal specimen culture

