#### **4.0 PATHOGEN IDENTIFICATION**

All microbiology data will be reviewed by the Sponsor for pathogen identification. A pathogen is defined as bacteria implicated as causative in a subject's CABP and will be determined separately for each subject. Baseline pathogens and post-baseline pathogens will be identified.

Additional details regarding the pathogen review process and determination are included in the Evaluability Review Plan.

Baseline for microbiologic specimens is defined as the 24-hour period prior to the administration of the first dose of study drug and the 24 hours after the first dose of study drug. A pathogen identified from a respiratory (pleural fluid, bronchoalveolar lavage (BAL), sputum), blood for culture, urine, nasopharyngeal or oropharyngeal specimen collected at baseline is considered a baseline pathogen. An atypical pathogen identified by serology is considered a baseline pathogen if the baseline sample is collected in the 24-hour period prior to the administration of the first dose of study drug or the 24 hours after the first dose of study. A Gram stain from a specimen collected at baseline is considered a baseline Gram stain.

If more than 1 specimen is taken during the baseline period, all specimens will be reviewed for pathogen identification. If the same pathogen (based on genus and species) is identified from more than 1 specimen, the pathogen with the highest minimum inhibitory concentration (MIC) to study drug received will be considered the baseline pathogen. If the pathogens have the same MIC to study drug received, the one with the highest accession number will be considered the baseline pathogen.

Post-baseline is defined as the period starting 24 hours after the first dose of study drug. A pathogen identified from a specimen collected post-baseline is considered a post-baseline pathogen. Only pathogens identified by culture of the sputum, BAL, pleural fluid or blood are considered post-baseline pathogens.

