### 4.3 Other Diagnostic Methods

Real-time quantitative Polymerase chain reaction based methods will also be used to determine the etiology of CABP at baseline.

- Frozen sputum samples will be analyzed by RQ-PCR using specific and conserved primers for the target genes based on current published studies (see [Table 1](#)). Single-plex RQ-PCR will be set up, validated and sputum samples will be analyzed by a specialized Good Laboratory Practices-certified bioanalytical laboratory (Accelero Bioanalytics GmbH, Germany).
- Oropharyngeal specimens will be analyzed by a specialized laboratory ([name], Diagnostic Mycoplasma Laboratory, UAB, AL, USA) using RQ-PCR for *Mycoplasma pneumoniae* (*repMp1*) and for detection of macrolide-resistance (23S rDNA).
- Nasopharyngeal specimens will be analyzed by a specialized laboratory ([name], Emory University, GA, USA) using RQ-PCR for detection of *S. pneumoniae* (*lytA*).

Amplified genes and cut-off values for the definition of a pathogen from the oropharyngeal and nasopharyngeal swabs are presented in [Table 1](#).

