**Table 1. Amplified Genes and Cut-off Values for RQ-PCR**

Specimen / Organism	PCR	Proposed Amplified gene a	Cut-off values for consideration of the organism as definite etiological significant for CABP	
			Cut-off values	Reference
Sputum				
S. pneumoniae	RQ-PCR	lytA	DNA corresponding to $\geq 10^4$ CFU/mL	Albrich et al, 2014
H. influenzae	RQ-PCR	frdB	DNA corresponding to $\geq 10^6$ CFU/mL	Johansson et al, 2010; Kais et al, 2006
M. catarrhalis	RQ-PCR	copB	DNA corresponding to $\geq 10^6$ CFU/mL	Johansson et al, 2010; Kais et al, 2006
S. aureus	RQ-PCR	nuc	DNA corresponding to $\geq 6 \times 10^5$ CFU/mL	Huang et al, 2015
M. pneumoniae	RQ-PCR	CARDS TX gene	Positive	Thurman et al, 2011; Waites et al, 2012
L. pneumophila	RQ-PCR	ssrA	Positive	Thurman et al, 2011
C. pneumoniae	RQ-PCR	argR	Positive	Thurman et al, 2011
Oropharyngeal swabs				
M. pneumoniae	RQ-PCR	repMp1	Positive	Thurman et al, 2011; Waites et al, 2012
Nasopharyngeal swabs				
S. pneumoniae	RQ-PCR	lytA	$\geq 1 \times 10^3$ CFU/mL	Chochua et al, 2015

a RQ-PCR will amplify the proposed genes provided that the validation is successful. If the RQ-PCR for the proposed target gene cannot be validated, another gene target will be used.

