### 5.5 Microbiological ITT-2 (microITT-2) Analysis Set

The microITT-2 Analysis Set will consist of all subjects in the ITT Analysis Set who have at least 1 baseline bacterial pathogen known to cause CABP as defined in Sections 4.1 and 4.2 from a diagnostic method other than PCR. Thus, the following will *not* be considered pathogens for the microITT-2 Analysis Set:

- *Streptococcus pneumoniae* from RQ-PCR of nasopharyngeal swab
- *Streptococcus pneumoniae*, *Haemophilus influenzae*, *Staphylococcus aureus*, or *Moraxella catarrhalis* from RQ-PCR of sputum
- *Legionella pneumophila*, *Mycoplasma pneumoniae*, or *Chlamydomphila pneumoniae* from RQ-PCR of sputum
- *Mycoplasma pneumoniae* from RQ-PCR of oropharyngeal swab

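### SAP 4.1 counts any positive nasopharyngeal culture as *S. pneumoniae* CABP, and no microbiological analysis set, not even microITT-2, removes subjects who qualify by that route alone

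*SAP*

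**What the plan says.** SAP 4.1 names four typical species, *S. pneumoniae* among them, each of which "will always be considered a CABP pathogen in the presence of the following criteria". The criteria for *S. pneumoniae* are alternatives, and the last is "Positive nasopharyngeal specimen culture". Nothing is attached to it.

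Two neighbouring criteria do carry a condition:

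- Sputum culture counts as "Positive sputum culture in the presence of a Gram stain with >25 PMNs/LPF and <10 SECs/LPF".
- PCR of a nasopharyngeal swab or sputum counts only at the cut-off in SAP Table 1, which for the nasopharyngeal swab is ≥1×10³ CFU/mL. The table column is headed "Cut-off values for consideration of the organism as definite etiological significant for CABP", and SAP 4.3 describes the table as giving the "cut-off values for the definition of a pathogen from the oropharyngeal and nasopharyngeal swabs are presented in" that table.

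SAP 4.0 confirms that a finding from a "nasopharyngeal or oropharyngeal specimen collected at baseline is considered a baseline pathogen". SAP 5.5 defines microITT-2 by removing PCR findings, including *S. pneumoniae* "from RQ-PCR of nasopharyngeal swab". It does not mention nasopharyngeal culture.

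**The concern.** A nasopharyngeal swab samples the upper airway, where *S. pneumoniae* can be carried without causing the pneumonia. For PCR on that site, the SAP asks for a minimum density before it treats the organism as the cause. For culture on the same site it asks for nothing further and gives no reason for the difference. Some subjects labelled as pneumococcal CABP may therefore be carriers whose pneumonia has another cause.

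The set that looks like a stricter check does not help. microITT-2 drops a nasopharyngeal PCR result at or above the cut-off but keeps an unquantified culture from the same site.

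At stake is how far the microITT, ME and *S. pneumoniae* by-pathogen results can be read as evidence in confirmed bacterial disease. If carriers dilute those sets, treatment differences there may look smaller than they are, which is the unfavourable direction for a non-inferiority reading.

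**Working it through.** The plan gives no figure on this point to reproduce. The check traces the rule through the analysis sets and then illustrates the possible effect.

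**Step 1: does any set remove these subjects?**

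| Set (SAP section) | What it requires or removes | Nasopharyngeal-culture-only subject |
|---|---|---|
| microITT (5.4) | any pathogen meeting 4.1 or 4.2 | kept |
| microITT-2 (5.5) | the same, without PCR findings | kept |
| ME (5.7) | microITT plus CE; removes resistant-only infections | kept if clinically evaluable |
| emicroITT (5.8) | relaxes only the sputum Gram-stain rule | kept |

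The blinded case-by-case review in SAP 4.1 is for isolates outside the named species, so it does not reach *S. pneumoniae*.

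**Step 2: which results use these sets?**

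- Not affected: ECR in ITT (SAP 8.5.1), and IACR in mITT and CE-TOC (SAP 8.5.3.1). Pathogen status does not define those sets. The power figures in SAP Table 7 concern only these three sets.
- Exposed: ECR in microITT, IACR in microITT and ME-TOC, and by-pathogen microbiological response, all secondary outcomes in SAP 6.2. The ECR and IACR tables by baseline pathogen are also exposed. SAP 8.5.3.2 gives microITT ECR a confidence interval only, but Protocol 9.6.2 plans a formal non-inferiority test of it in data pooled with a second study.

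**Step 3: possible size.** Let d be the true difference (lefamulin minus moxifloxacin) in correctly classified subjects, f the share of the analysed group who qualify by nasopharyngeal culture alone, and c the difference in those subjects, with f equal in both arms. Then

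observed difference = (1 − f) × d + f × c.

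Neither f nor c is in the documents. With c = 0, for assumed values of d and f:

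| d (points) | f = 5% | f = 10% | f = 20% | f = 30% |
|---|---|---|---|---|
| −10 | −9.5 | −9.0 | −8.0 | −7.0 |
| −12.5 | −11.9 | −11.3 | −10.0 | −8.8 |
| −15 | −14.3 | −13.5 | −12.0 | −10.5 |

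For example, 0.90 × (−12.5) = −11.25. If c equals d there is no dilution at all.

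**Step 4: which share applies.** In the *S. pneumoniae* tables, f is the share of *S. pneumoniae* subjects with no other evidence of that species. For microITT as a whole, f counts only subjects with no other qualifying pathogen or method, divided by all microITT subjects. If *S. pneumoniae* subjects are a fraction s of microITT and a fraction g of them have no other route in, then f = s × g. This cannot exceed g, and it is smaller than g whenever microITT contains other pathogens.

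**The case against.** A reader might infer from Table 1 that a nasopharyngeal finding has causal weight only at ≥1×10³ CFU/mL, so that the culture criterion contradicts the SAP. The documents do not support that. Table 1 is a table of PCR targets and cut-offs and makes no statement about culture. Sputum culture has no density limit either: its Gram-stain rule tests specimen adequacy, and a sputum culture can qualify without reaching the 10⁴ CFU/mL set for sputum PCR. Method-specific criteria are legitimate. What stands is narrower: nasopharyngeal culture has neither a density nor a quality condition, and no reason is given.

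How often a swab grows the organism yet falls below the PCR cut-off is unknown. Swabs are frozen before shipment (Protocol 6.15.8), and no positivity or carriage rates are given. This objection stands in full.

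Equal outcomes in the two arms among carriers cannot be taken for granted. Their pneumonia may be due to another bacterium against which the two drugs also differ. Known viral, fungal and noninfectious causes are excluded at entry (Protocol 4.2) and, if found later, from CE and hence ME (SAP 5.6). This stands, so the pull toward zero is conditional.

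SAP 8.3 will tabulate baseline pathogens by diagnostic modality and arm. That shows how many subjects had a positive nasopharyngeal culture, but not how many had nothing else. SAP 4.0 also refers to an Evaluability Review Plan, which is not among the documents and might add a rule, although the automatic wording of SAP 4.1 leaves it little room.

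**Conclusion.** The gap is real and limited. Nasopharyngeal culture alone is sufficient for *S. pneumoniae* CABP under SAP 4.1, and no planned set tests whether results depend on it. The consequence is confined to secondary and by-pathogen results. The most important is microITT ECR, because of the pooled test in Protocol 9.6.2, for which no separate margin is stated.

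It would be going too far to conclude that the trial's main non-inferiority claim is biased: the ITT, mITT and CE-TOC analyses do not use pathogen status. It would also be wrong to apply an assumed 10% to 30% share of *S. pneumoniae* subjects to microITT as a whole, where the relevant share is no larger and probably smaller. By-pathogen microbiological response is only tabulated (SAP 8.5.3.4), and the additional analyses carry no non-inferiority conclusion (SAP 8.5.4).

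Any dilution is proportional to the share who qualify by this route alone: with no treatment difference in those subjects, each 10% removes a tenth of the true difference. Both that share and the absence of a difference are assumptions.

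**What to change.** Amend the SAP before database lock, as SAP 1.0 allows, in one of two ways:

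- Add *S. pneumoniae* identified by nasopharyngeal culture only to the findings that do not count in microITT-2 (SAP 5.5). That list works on findings, so a subject with another qualifying non-PCR finding stays in. microITT and ME are unchanged.
- Or count such cases only in emicroITT. This changes microITT (SAP 5.4) and, through it, ME.

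At minimum, report by arm the number of subjects with no other qualifying pathogen or method, and repeat without them ECR in microITT, IACR in microITT and ME-TOC, and the *S. pneumoniae* by-pathogen response in both sets. This is also the cleanest check, because a comparison of microITT with an amended microITT-2 would mix the removal of PCR findings with the removal of nasopharyngeal cultures.

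Do not make the PCR cut-off a condition for culture. A swab that reaches it already qualifies under the preceding criterion, so the culture criterion would add nobody to microITT, and a PCR result would become the gatekeeper of a set defined without PCR.

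The cost is wording and a few extra tables. One screening swab already serves both culture and PCR (Protocol 6.15.8), so no new sampling is needed. The downside is somewhat fewer *S. pneumoniae* subjects in the stricter set.

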### *Haemophilus influenzae*

- Positive BAL, pleural fluid or blood culture; or
- Positive sputum culture in the presence of a Gram stain with >25 PMNs/LPF and <10 SECs/LPF (**NOTE:**  $\geq 10$  PMNs/LPF and <10 SECs/LPF in the emicroITT Analysis Set); or
- Positive RQ-PCR of sputum (see [Table 1](#) for cutoff value); or

### *Staphylococcus aureus*

- Positive BAL, pleural fluid or blood culture; or
- Positive sputum culture in the presence of a Gram stain with >25 PMNs/LPF and <10 SECs/LPF (**NOTE:**  $\geq 10$  PMNs/LPF and <10 SECs/LPF in the emicroITT Analysis Set); or
- Positive RQ-PCR of sputum (see [Table 1](#) for cutoff value)

### *Moraxella catarrhalis*

- Positive BAL, pleural fluid or blood culture; or
- Positive sputum culture in the presence of a Gram stain with >25 PMNs/LPF and <10 SECs/LPF (**NOTE:**  $\geq 10$  PMNs/LPF and <10 SECs/LPF in the emicroITT Analysis Set); or
- Positive RQ-PCR of sputum (see [Table 1](#) for cutoff value)

The following isolates are considered as contaminants from respiratory specimens rather than primary pathogens of CABP: fungi, *Enterococcus* spp., viridans streptococci, coagulase-negative staphylococci, *Micrococcus* spp., *Neisseria* spp. other than *N. meningitidis*, *Corynebacterium* spp. and other coryneforms, *Lactobacillus* spp., *Vibrio* spp., *Capnocytophaga* spp., *Cardiobacterium* spp., *Flavobacterium* spp.

Other isolates identified from culture of blood and respiratory specimens will be reviewed in a blinded manner by the Sponsor on a case-by-case basis for determination of whether the organism is a pathogen for CABP.

## **4.2 “Atypical” Respiratory Pathogens**

*Legionella pneumophila*, *Mycoplasma pneumoniae*, and *Chlamydia pneumoniae* will always be considered a CABP pathogen in the presence of the following criteria:

### *Legionella pneumophila*

- Positive BAL, pleural fluid or blood culture; or
- Positive sputum culture, regardless of Gram stain findings; or
- Positive urinary antigen test; or

- Between baseline and convalescent (LFU Visit) specimens, a 4-fold or greater increase in *L. pneumophila* antibody titer to  $\geq 1:128$ ; or
- Positive RQ-PCR of sputum

***Mycoplasma pneumoniae***

- Between baseline and convalescent (LFU Visit) specimens, a 4-fold or greater increase in *M. pneumoniae* IgG serum antibody titer to  $\geq 1:160$ ; or
- Positive oropharyngeal specimen culture; or
- Positive BAL, pleural fluid or blood culture; or
- Positive sputum culture in the presence of a Gram stain with  $>25$  PMNs/LPF and  $<10$  SECs/LPF (**NOTE:**  $\geq 10$  PMNs/LPF and  $<10$  SECs/LPF in the emicroITT Analysis Set); or
- Positive RQ-PCR of oropharyngeal swab or sputum (see [Table 1](#) for cutoff values)

***Chlamydia pneumoniae***

- Between baseline and convalescent (LFU Visit) specimens, a 4-fold or greater increase in *C. pneumoniae* IgG serum antibody titer; or
- Positive RQ-PCR of sputum

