#### 6.15.5 Serological Testing

Blood samples will be collected at Screening and LFU, and sent frozen to the central laboratory for serologic tests for *M. pneumoniae*, *C. pneumoniae*, and *L. pneumophila*.

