### 5.4 Microbiological ITT (microITT) Analysis Set

The microITT Analysis Set will consist of all subjects in the ITT Analysis Set who have at least 1 baseline bacterial pathogen known to cause CABP as defined in Sections 4.1 and 4.2. Additional isolates not a priori defined as pathogens in this SAP will be evaluated on a case by case basis by the Evaluability Review Team.

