## 7.6 Handling of Missing Data

For ECR, missing data will be handled as follows:

- If any component of ECR is missing in the time frame detailed in Section 6.1 (unless the subject dies or is deemed a failure prior to this time point), or if the subject does not have at least 2 symptoms of CABP at baseline, ECR will be defined as an indeterminate.
- If the time of a post-baseline assessment of CABP symptoms obtained in the window for determination of ECR is missing but the date of the ECR assessment is known, the time will be imputed to noon on the date of the CABP symptom assessment. If the time of assessment of CABP symptoms obtained on or prior to the date of the first dose of study drug is missing, the time will be imputed to 00:00.
- Missing start and stop times of antibiotics will be set to 00:00 on the start and stop date of the antibiotic.
- For the analysis of ECR in the ITT Analysis Set, where ECR may be missing (indeterminate), all subjects in the ITT Analysis Set will be included in the denominator. Thus, subjects with an indeterminate response are essentially considered as a failure.

For IACR, missing data will be handled as follows:

- A missing IACR at the EOT Visit will be considered indeterminate at the EOT Visit.
- A missing IACR at the TOC Visit will be considered indeterminate unless the IACR at the EOT Visit is failure. An IACR of failure at the EOT Visit will be carried forward to the TOC Visit.
- A missing IACR at the LFU Visit will be considered indeterminate unless the IACR at the TOC Visit is failure. An IACR of failure at the TOC Visit will be carried forward to the LFU Visit.
- For the analysis of IACR at the EOT, TOC and LFU Visits in the mITT, microITT, microITT-2 and emicroITT Analysis Sets, where Clinical Response may be missing (indeterminate), all subjects who meet the analysis set criteria will be included in the denominator.
- For the analysis of IACR at the EOT, TOC and LFU Visits in the CE and ME Analysis Sets, subjects with a missing (indeterminate) IACR will not be included in the analyses, since by definition, subjects in the CE or ME Analysis Sets cannot have a missing IACR.

For microbiological response, missing data will be handled as follows:

- If a followup specimen for culture was not obtained, microbiological response at the EOT Visit will be determined based on the IACR at the EOT Visit.

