- d: Perform End of Treatment (EOT) assessments at the study site within 1 day (up to 2 days permitted) after the last dose of study drug or at the time of premature discontinuation of study drug or early withdrawal from study. EOT assessments resulting from premature discontinuation of study drug should be done in place of the regular study visit on Days 1 to 7.
- e: Perform Test of Cure (TOC) assessments at the study site 5–10 days after the last dose of study drug. All subjects will have a TOC Visit irrespective of early clinical failure or receipt of an alternative antibiotic.
- f: Perform Late Follow Up (LFU) assessments at the study site on Day 30 ± 3 days. All subjects will have a LFU Visit irrespective of early clinical failure or receipt of an alternative antibiotic.
- g: Obtain informed consent before initiating any study-specific assessments or procedures.
- h: Assessment or procedure may occur at either Screening OR prior to the first dose of study drug on Day 1 once eligibility has been determined.
- i: All subjects will have vital signs and O2 saturation evaluated at Screening/Baseline and Day 1. If screening/baseline and Day 1 occur on the same calendar day, vital signs and O2 saturation do not need to be repeated. All subjects will also have assessments at EOT and TOC; at LFU, vital signs should be performed if medically indicated. If EOT and the last day of study drug are the same day, vital signs do not need to be repeated, they may be recorded once on that day (i.e., as part of the EOT assessment). Record the vital signs associated with the highest temperature after the first dose of study drug.  
**INPATIENTS:** Vital signs, O2 saturation, and supplemental O2 usage will be measured daily. If multiple vital signs are taken on a study day, the highest temperature and the vital signs associated with that high temperature will be recorded.  
**OUTPATIENTS:** In addition to the above time points, vital signs, O2 saturation and, if applicable, supplemental O2 usage will be measured at the study visit scheduled 96 ± 24 hours after the first dose of study drug.

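### Paired serology needs a Day 30 serum, so serology-only atypical cases who die or are lost before LFU never enter the microITT-type sets

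*SAP*

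**What the plan says.** SAP 4.2 lists alternative criteria for each atypical organism. The serological one is the same in form for all three: "Between baseline and convalescent (LFU Visit) specimens, a 4-fold or greater increase in" antibody titre, with a minimum final titre for *L. pneumophila* and *M. pneumoniae*. The only sampling times are in Protocol 6.15.5: "Blood samples will be collected at Screening and LFU, and sent frozen to the central laboratory for serologic tests". SAP Appendix A sets the second one: "Perform Late Follow Up (LFU) assessments at the study site on Day 30 ± 3 days". No convalescent draw is scheduled at EOT, TOC or early withdrawal, and SAP 7.6 has no rule for a missing convalescent serum.

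SAP 5.4 admits a subject to microITT with "at least 1 baseline bacterial pathogen known to cause CABP as defined in Sections 4.1 and 4.2". The emicroITT set (SAP 5.8) changes only the Gram-stain threshold for sputum culture. The microITT-2 set (SAP 5.5) requires a pathogen "from a diagnostic method other than PCR", so it keeps serology.

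Within these sets the plan is strict about missing outcomes. SAP 6.2.1 makes death a Failure at EOT and TOC and puts indeterminates in the success-rate denominator. For IACR in the ITT-type sets, SAP 7.6 says that "all subjects who meet the analysis set criteria will be included in the denominator".

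**The concern.** A pathogen that the SAP calls baseline is, on this one route, established only if the subject survives and is retained to about Day 30. Take two subjects with identical *Mycoplasma* infection, each detectable only by titre rise. One recovers, gives an LFU serum and enters microITT as a success. The other dies on Day 12 or is lost before TOC, has no second serum and so no baseline pathogen, and never reaches the denominator in which SAP 6.2.1 and 7.6 would have counted a non-success.

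The microITT set carries secondary outcomes: ECR, IACR at TOC and by-pathogen response (SAP 6.2). It also carries LFU outcomes overall and by pathogen (SAP 6.3, 8.5.4). Protocol 9.6.2 places a formal pooled two-study non-inferiority test of ECR in it. No planned set removes serology-only pathogens. The microITT-2 set is more exposed than microITT: with PCR removed, paired serology is the only route that SAP 4.2 lists for *C. pneumoniae*.

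**Working it through.** The plan gives no figure to reproduce here. It states neither the proportion of serology-only cases, nor the proportion without an LFU serum, nor outcomes among those without one. The check is therefore an illustration over stated ranges.

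**Inputs**
- S, true success rate: 80%, borrowed from the mITT planning rate for IACR at TOC in SAP 7.1.
- f, share of the denominator in question that is detectable by serology alone: assumed 10% to 100%. The top value is *C. pneumoniae* in microITT-2.
- m, share of serology-only cases without an LFU serum: assumed 3% to 10%.
- p0, success rate among those without an LFU serum: assumed 0 to 90%.
- Serology-only cases are assumed to share the overall rate S.

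**Bias in one arm's rate.** The rule removes a fraction f·m of the denominator, whose success rate is p0:

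observed = (S − f·m·p0) / (1 − f·m), so bias = f·m·(S − p0) / (1 − f·m).

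For f = 0.3, m = 0.10, p0 = 0: 0.80 / 0.97 = 82.47%, or +2.47 points.

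| f | p0 | m = 3% | m = 5% | m = 10% |
|---|---|---|---|---|
| 0.1 | 0 | +0.24 | +0.40 | +0.81 |
| 0.3 | 0 | +0.73 | +1.22 | +2.47 |
| 0.5 | 0 | +1.22 | +2.05 | +4.21 |
| 1.0 | 0 | +2.47 | +4.21 | +8.89 |
| 1.0 | 50% | +0.93 | +1.58 | +3.33 |
| 1.0 | 80% | 0 | 0 | 0 |
| 1.0 | 90% | −0.31 | −0.53 | −1.11 |

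The sign is that of S − p0, so it depends on the endpoint:
- **Sustained success at LFU.** In microITT a subject with no LFU visit is a relapse (death), a prior failure or an indeterminate, never a sustained success (SAP 6.2.1). So p0 = 0, apart from visits held without a blood draw, and the bias is upward.
- **IACR at TOC.** Death or loss before TOC is a non-success, which lowers p0. A TOC success lost between TOC and Day 30 is also removed, which raises it. Upward bias is likely, not certain.
- **ECR.** The assessment window closes at 120 hours (SAP 6.1). A subject lost later may well be a responder, so the sign is open.

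**Bias in the treatment difference.** If f, m and p0 are equal in both arms, the p0 terms cancel and observed difference = true difference / (1 − f·m). Example in serology-only subjects (f = 1), m = 12%, p0 = 40%, rates under the rule 80% and 88%: the true rates are 0.88 × 80 + 0.12 × 40 = 75.2% and 0.88 × 88 + 0.12 × 40 = 82.2%. The true difference is −7.0 points and the rule reports −8.0.

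If loss differs, say 3% in one arm and 6% in the other with p0 = 0, the spurious difference is 0.80 / (1 − 0.06f) − 0.80 / (1 − 0.03f): 0.24, 0.74, 1.26 and 2.63 points for f = 0.1, 0.3, 0.5 and 1.

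**The case against.** The strongest reply is that few subjects can be lost this way. Serology is one of several alternatives, and one pathogen by any listed method is enough for microITT. *Legionella* can also enter by culture, sputum PCR or "Positive urinary antigen test; or"; *Mycoplasma* by culture or by PCR of an oropharyngeal swab or sputum. Failure alone does not remove anyone: "All subjects will have a LFU Visit irrespective of early clinical failure or receipt of an alternative antibiotic". A surviving failure can show a titre rise and count as a failure. SAP 8.3 already tabulates pathogens by diagnostic modality. The single-study microITT results are confidence intervals, and the plan for the pooled test is not in these documents.

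Most of this stands, and it limits the point to subjects with no other positive test. A subject positive for another organism stays in the set but is still missing from the atypical organism's row. The SAP 8.3 table reports pathogens, not outcomes, by modality, and it does not isolate serology-only cases. Serology-identified pathogens can have only a presumed or indeterminate microbiological response (SAP 6.2.3), so later cultures do not correct their by-pathogen results.

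Three stronger readings are tempting, and the documents support none of them. A reader might infer that everyone who dies or drops out leaves microITT; any other positive baseline test keeps them in. A reader might infer that atypical success rates are certainly inflated; at ECR and TOC the sign depends on p0. A reader might infer that the treatment difference is pulled toward zero, flattering non-inferiority; equal loss with equal outcomes among the lost widens it instead.

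**Conclusion.** The point holds for one group: subjects whose sole pathogen evidence would be the baseline-to-LFU titre rise. For them, entry to microITT, microITT-2, emicroITT and the by-pathogen denominators depends on survival and retention to Day 30, against the plan's own treatment of deaths and indeterminates. No planned analysis checks this.

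With S = 80%, m = 3-10% and p0 = 0, the overstatement is about 0.7 to 2.5 points if 30% of an organism's cases are serology-only. It reaches about 9 points if all are, as can happen for *C. pneumoniae* in microITT-2. These inputs are assumptions, and p0 = 0 is the extreme case except at LFU, where it follows from the outcome definition. The treatment difference is biased mainly if LFU loss, or outcomes among those lost, differ by arm.

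Primary ECR in ITT, and IACR in mITT and CE-TOC, do not use pathogen status and are unaffected.

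**What to change.** Add a supplementary microITT analysis of ECR, IACR at TOC and LFU, and by-pathogen response that excludes pathogens whose only evidence is paired baseline/LFU serology. Name it as the check on the microITT result and on this study's contribution to the pooled microITT test of ECR. In the by-pathogen tables, show serology-only atypical pathogens on a separate row. Report missing LFU sera by arm for all randomized subjects, because the microITT sets cannot show who failed to enter them.

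Define the exclusion by the type of evidence. Limiting it to specimens from the SAP 4.0 baseline window would not work: that section counts a serological pathogen as baseline whenever the first serum falls in the window.

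The cost is SAP wording, one flag and one table set; diagnostic modality is already needed for SAP 8.3. The supplementary version will hold fewer atypical pathogens, will drop true cases among survivors, and will leave *C. pneumoniae* resting on sputum PCR alone. It should therefore sit beside the planned analysis and not replace it.
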